336 We will conduct a qualitative sub-study to understand patients' and clinicians' acceptability and
337 satisfaction with the intervention and explore components which may need to be changed. The
338 qualitative evaluation will be in the form of phone or face to face interviews at the end of the 6
339 month follow-up.
340

341 7. Study population

342 We will recruit adult participants who have been treated for a first primary melanoma, stage 0/I/II,
343 and who are undergoing regular melanoma follow-up at recruiting melanoma and skin cancer
344 clinics in NSW.
345

346 This pilot study aims to recruit 100 patients from the Melanoma Institute Australia (MIA) and Royal
347 Prince Alfred Hospital (RPAH) (specialist treatment centres) and the Newcastle Skin Check clinic
348 (GP run clinic). Recruitment will be done over six months.
349

350 7.1. Inclusion Criteria

- 351 • Patients treated for stage 0/I/II melanoma who are attending regular melanoma follow-up as
352 indicated by scheduled or recommended visit within next 12 months.
353 • Are able to self-examine;
354 • Have a suitable study partner (spouse, partner, family member, friend) to help with self-
355 examination
356 • Own a compatible Smartphone (and have access to Wifi / email / SMS text messaging);
357 • Are able to give informed consent;
358 • Have sufficient English language skills to read the materials and complete the
359 questionnaires;
360 • Aged 18+ years old.

361 7.2. Exclusion Criteria

- 362 • unable to perform self-examination
363 • Patient who currently or previously have had stage III/IV melanoma
364 • Patients with a known past or current diagnosis of cognitive impairment

365 8. Study procedures

366 8.1. Enrolment procedure

367 All patients treated for localised melanoma who are attending regular follow-up, will be identified in
368 clinic by the clinician. The potential participant will be contacted by a research coordinator who will
369 explain the study and give the patient an invitation package either in person or by mail. The initial
370 study invitation package includes: Study Invitation Letter, Participant Information Sheet, Consent
371 Form, Participation Card, Baseline Questionnaire (to measure demographics, knowledge, attitudes
372 and confidence on self-examination and smartphone Apps, and their baseline level of fear of new
373 or recurrent melanoma (using a melanoma specific version of the Fear of Cancer Recurrence

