408 Participants allocated to the intervention will receive:

- 409 • An educational booklet 'Your guide to early melanoma',
- 410 • Web-based ASICA skin checker log-in. The web-based ASICA skin checker combines
411 instructional videos, guided total skin self-examination and electronic reporting,¹⁵
- 412 • A dermatoscope to attach to their phone similar to that reported in *Manahan et al.*¹⁶.
- 413 • Detailed written instructions on how to use the smartphone App and dermatoscope.

- 414 • Video outlining how to use the dermatoscope and associated App/online submission
 415 platform.
 416 • Email or SMS text reminders every 2 months to perform SSE.
 417 • Teledermoscopy: participants are required to take dermoscopic images of at least 3 lesions
 418 and up to 9 lesions on each SSE, including all lesions that concern them, and submit these
 419 through the smartphone App. They are also required to enter a text description of the results
 420 of SSE for each part of the body and submit this through the web-based ASICA skin
 421 checker. Both dermoscopic images and text reports will be sent securely to one of the study
 422 dermatologists, who will undertake teledermatology review within 3 days and feedback the
 423 results to the participant.
 424 • Unscheduled visits as needed in addition to those prompted through Teledermatology.
 425 • Scheduled visits as per treating clinician.
 426

427 Those allocated to the control arm will receive:

- 428 • An educational booklet 'Your guide to early melanoma';
 429 • Unscheduled visits as needed
 430 • Scheduled visits as per treating clinician
 431

432 All participants will receive two study questionnaires; one at baseline and one at 6 months.
 433

434 **8.4. Blinding**

435 Blinding of participants, site staff and treating clinicians will not be possible in this trial. Where
 436 possible, outcome assessment will be done masked to study group allocation.
 437

438 **8.5. Duration of treatment/ Study**

439 Unless the study is closed prematurely, it will proceed to the pre-defined accrual target. Following
 440 announcement of closure to recruitment by the research team, no further enrolment will be
 441 possible. It is anticipated, based on estimates from individual sites that the accrual target will be
 442 reached over a period of 6 months. Each participant will be followed up for 6 months. The timeline
 443 below provides an outline of anticipated study milestones:
 444
 445

Timeline	2017	2018	2019	2020

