531 rostered on to review the reports and images of patient detected lesions, and feedback
532 recommendations to the patient as to the action that needs to be taken. They will report
533 results within 3 working days of receiving the electronic text report and images from the
534 patient. If the report is not reviewed in this timeframe the site study coordinator will notify the
535 patient of a delay in reporting. They will provide one of the following recommendations:
 - 536 ○ Follow Up Photo - There is no immediate concern today, but this case should
537 continue to be monitored. Please take another picture and resubmit for review.
 - 538 ○ Retake Photo - Unfortunately, the image quality is not sufficient for
539 teledermatology review. Please retake the photo.
 - 540 ○ Clinical Exam - We recommend that you book an appointment with your doctor
541 to examine this case. Please call your melanoma clinic to make an appointment
542 at your earliest convenience.
 - 543 ○ No Concern Today - This case does not seem to be suspicious at this time. Self-
544 monitor and review with your doctor at your next scheduled visit.
 - 545 ○ Biopsy/Excision - We recommend that you book an appointment with your doctor
546 to examine this case as biopsy or excision may be needed. Please call your
547 melanoma clinic to make an appointment at your earliest convenience.
 - 548 ○ Other
- 549 • Educational booklet ‘Your guide to early melanoma’: The freely available booklet developed
550 by the Melanoma Institute Australia for patient support and comprises a treatment-
551 management organiser and detailed information source in one booklet. Contents include: -
552 Diagnosis summary - Melanoma glossary - Treatment plan - Pain diary - Medication chart -
553 Body maps for self-examination - Frequently asked questions - Supportive services -
554 Information on treatments and surgical procedures
- 555 • Written and video instructions on how to use the dermatoscope + Smartphone App
- 556 • Email and/or SMS text reminders every 2 months to perform self-examination
- 557 • Unscheduled visits as needed in addition to those prompted through Teledermatology
- 558 • Scheduled visits as needed
- 559 • Monthly diaries capturing clinic visits and travel costs

560

561 The control arm comprises

- 562 • An educational booklet ‘Your guide to early melanoma’;
- 563 • Unscheduled visits as needed

- 564 • Scheduled visits as needed
565 • Monthly diaries capturing clinic visits and travel costs

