700 The proportion of patients who are randomised into the trial will be estimated using the number of
701 contacted patients as the denominator. The Wilson (score) method will be used to estimate the
702 confidence interval for this proportion to assess the best and worst case scenarios supported by the
703 pilot study data. We will investigate and describe any groups that had low participation rates in our
704 pilot study.

705

706

707 13.4.2. Statistical analysis for secondary endpoints

708 We will use a chi-squared test to investigate the difference in proportion undertaking regular skin
709 self-examination between the intervention arm and the usual care arm. A t-test will be used to
710 compare fear of new or recurrent melanoma severity at 6 months between the intervention and
711 usual care group. We will report any estimated differences (either proportions or means) with
712 appropriate confidence intervals as the power for these comparisons will be limited.

713

714 13.5. Secondary analyses**715 *Teledermatology Repeatability Study***

716 Sub-study to assess Dermatologist diagnostic agreement of electronic text reports and images
717 collected during the trial.

718 We will assess inter-rater agreement across three dermatologists, reporting on prospectively
719 collected Teledermatology materials. After close-out of the trial, three dermatologists (CIs [name],
720 [name] and [name]) will independently review all electronic reports and images of patient detected
721 lesions that they did not report on during the trial. All three dermatologists will report their results
722 blinded to those of the other two dermatologists and to any other clinical information apart from that
723 received during the Teledermatology (age and sex of patient and the text report describing the
724 lesion where this was provided).

725 Agreement across the following broad clinical diagnostic categories will be calculated:

- 726 • No concern today [i.e. benign]
- 727 • Follow up photo [i.e. low probability of melanoma/NMSC]
- 728 • Clinical Exam [i.e. intermediate probability of melanoma/NMSC]
- 729 • Biopsy/excision [i.e. high probability of melanoma/NMSC]
- 730 • Only one category per patient episode allowed, where teledermatologist makes more than
731 one diagnosis, most severe diagnostic category used.

732 We will construct cross-classification tables to separately compare inter-rater reliability for text

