733 report + macroscopic image and for text report + dermoscopic image. We will calculate percentage
734 agreement and kappa statistics across diagnostic categories and 95% confidence intervals for
735 these.

736

737 *Costing study*

738 We will identify, measure and value all resources used (micro-costing approach) to estimate the
739 total costs to patients, to the health system, and to the planet (carbon emissions) for the
740 intervention and control groups. All costs associated with SSE, skin surveillance and management

741 of newly identified lesions, out of-pocket costs, opportunity costs and carbon costs will be
742 included.²⁰

743 Patient diaries

744 Patient out-of-pocket and health system costs associated with each arm of the trial will be
745 estimated using a monthly resource use diary.^{21,22} The diary will be used to document and measure
746 health behaviours and service use - such as hospitalisation, other allied health consultations, use of
747 alternative therapies and self-monitoring behaviours. The diary will also record any melanoma
748 follow up consultations and procedures conducted by other providers (e.g. GPs). We will ask
749 patients to report the number of trips made to their melanoma follow-up clinic and the mode of
750 transport used. We will also ask patients to report any visits to other physicians in the community
751 for a skin lesion excision or other skin cancer related procedures. The time each patient spent to
752 perform digital SSE and to attend follow-up visits will be recorded. The diary will also document
753 carers' days out-of-role (including paid and unpaid work), travel costs and direct carer costs.

754 Review of medical records

755 All recorded melanoma follow up consultations and procedures will be extracted from the patients'
756 medical records in the clinic databases. We will also extract all diagnostic tests during the trial
757 period.

758 The mean (and standard deviation) volume of resource use by category and mean cost per
759 participant will be tabulated. The difference in resource use and costs between the intervention and
760 control groups will be presented with 95% CIs, and P- values for differences will be calculated by
761 two sample t-tests.

762 Carbon Costs

763 We will then apply a carbon value to each of the types of resource use identified above. This will
764 include direct estimation (e.g. travel) and indirect (e.g. life cycle costs of a tablet/smartphone). We

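### The costing study promises to cost all self-examination in both arms, but the only self-examination time it names is for digital examination, which only the intervention arm performs

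*Combined protocol and SAP*

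**What the plan says.** **Scope.** Section 13.5, Costing study, sets a micro-costing approach for the "intervention and control groups. All costs associated with SSE, skin surveillance and management" of newly found lesions, and adds out-of-pocket and opportunity costs. Section 6.2 says the same. The scope is complete and symmetric between arms.

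**Time item.** Under Patient diaries, section 13.5 names one item on time: "The time each patient spent to" "perform digital SSE and to attend follow-up visits will be recorded". It specifies no time on self-examination without the digital tools.

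**Who has the tools.** In section 8.3, "Web-based ASICA skin checker log-in", the dermatoscope and the App instructions are listed for the intervention arm only. Table 1 likewise ticks the dermatoscope, the App instructions and the survey code for that arm alone.

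**Controls self-examine too.** Section 7.1 requires every participant to be able to self-examine and to "Have a suitable study partner (spouse, partner, family member, friend) to help with self"-examination. The booklet given to both arms includes "Body maps for self-examination - Frequently asked questions" (section 10.1). Section 13.4.2 tests the difference in regular "self-examination between the intervention arm and the usual care arm".

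**Diary.** Table 1 sends it to both arms. M8 in section 12.2 and section 13.5 say that it covers self-monitoring behaviours, among other things. Section 10.1 describes it more narrowly, as covering clinic visits and travel costs.

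**The concern.** The plan undertakes to value a resource in both arms, but names a measurement that only one arm can supply. A control participant who spends half an hour with a partner and the booklet's body maps has used the same kind of resource as an intervention participant with the App. The stated item has no place for it.

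The cost difference is to be reported with a 95% confidence interval and a P-value (section 13.5). Aim 4 in section 6.1 is that patient-led surveillance decreases resource use and costs. Section 5.2 says that the pilot supports planning of a larger trial that will compare resource use. For those purposes the quantity wanted is the extra time that patient-led surveillance asks of patients, beyond what they would spend on self-examination anyway. A total for one arm, set against nothing in the other, does not give that. Minutes not collected during follow-up cannot be recovered afterwards.

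**Working it through.** The plan gives no figure on this point, so there is none to reproduce. The check sets the passages side by side and then derives the error.

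**Step 1: does any other item supply the missing minutes?**
- M2.1 (section 12.2) asks how often participants do a complete skin examination, not how long it takes.
- M8 and section 13.5 list self-monitoring behaviours, but do not say that their duration is recorded.
- Carer items are days out-of-role, travel costs and direct carer costs. A helper's minutes do not fit a unit of days.
- Section 10.1 mentions clinic visits and travel costs only.

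No passage names minutes of non-digital SSE, for the participant or the helper.

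**Step 2: what is the error if the stated item is followed literally?** Let D be mean digital SSE hours per intervention participant over six months. Let N_I and N_C be mean non-digital SSE hours in the intervention and control arms, and v the value of an hour.
- Reported difference (intervention minus control) in SSE time cost: v × D
- True difference: v × (D + N_I − N_C)
- Error, reported minus true: v × (N_C − N_I)

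D cancels. The error depends only on the between-arm difference in non-digital time. It counts against the intervention when N_C exceeds N_I, is zero when they are equal, and reverses when N_I is larger.

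**Step 3: illustration.** The documents give no control-arm frequency, no minutes per examination and no hourly value. Assumed: 1 to 6 control examinations in six months, 10 to 30 minutes each, v of AU$20 to AU$40 per hour.

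| Control-arm non-digital SSE | N_C (hours) | Error if N_I = 0 | Error if N_I = N_C/2 |
|---|---|---|---|
| 1 × 10 min, AU$20/h | 0.167 | AU$3.33 | AU$1.67 |
| 3 × 20 min, AU$20/h | 1.0 | AU$20 | AU$10 |
| 3 × 20 min, AU$40/h | 1.0 | AU$40 | AU$20 |
| 6 × 30 min, AU$40/h | 3.0 | AU$120 | AU$60 |

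If N_I were 1.5 hours against N_C of 1.0 hour, the error at AU$20/h would be 20 × (1.0 − 1.5) = −AU$10, in favour of the intervention. The table shows how the error behaves; it does not estimate its size in this trial.

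**Step 4: which direction is likelier?** Intervention participants are reminded every two months and must report on each body part through the web tool (sections 8.3 and 10.1). Much of their self-examination should therefore be digital, and all of the controls' is non-digital. N_C above N_I is plausible, but nothing in the documents establishes it.

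**The case against.** The strongest reply is that the stated scope already covers this. Section 13.5 commits to all SSE and opportunity costs in both groups, the diary covers self-monitoring behaviours in both arms, and the time sentence refers to each patient without naming an arm. The diary form is not in the documents, so it may already ask controls for minutes. This stands as far as it goes. A reader might infer that control-arm SSE time is not collected, or is valued at zero; no passage says either. What remains is that the plan names duration for digital SSE and for no other kind, so the commitment is not matched by a stated measurement.

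A reader might also infer that the bias certainly runs against the intervention. The documents do not support that: intervention participants receive the same booklet and may examine themselves between reminders, and that time would be missed too.

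It is tempting to size the omission from the two figures in section 5.1 (14%, and less than half). They report how many respondents examined all parts of the body, which is thoroughness, and cannot serve as the share of controls examining every two months.

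On helper time, the partner requirement applies to both arms, so the requirement alone shows no imbalance. The gap there is completeness: the carer units are too coarse for minutes.

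Finally, this is one component of a secondary analysis in a pilot of 100 people, and no passage says that SSE time costs will be carried into the larger trial as such. That limits the importance of the point but does not remove the mismatch.

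**Conclusion.** The point holds as a mismatch between scope and measurement. All SSE is to be costed in both arms, but the only SSE time named is digital, which only the intervention arm performs. If the diary follows that wording, the SSE part of the patient time cost difference is the gross digital time, and the error is v × (N_C − N_I). It probably leans against the intervention.

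Its size cannot be determined from the documents. The illustrative AU$3 to AU$120 per participant rests wholly on the assumed frequencies, minutes and hourly values and on no non-digital SSE in the intervention arm. It has not been set against total cost, which also includes visits, procedures and travel.

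The conclusion depends on the diary following the text of section 13.5. If the form already asks both arms for minutes on any SSE, only the wording needs correcting. The effect is confined to a secondary costing outcome. The primary outcome, the proportion of invited patients who are randomised, is unaffected. The change is worth making because it is cheap and the data cannot be recovered later.

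**What to change.** 1. In both arms, word the diary item as minutes spent this month on any skin self-examination, with or without the App.
2. Add a line for the helper's minutes.
3. State in section 13.5 that these minutes are valued in the same way in both groups.
4. Keep digital SSE time as a sub-item in the intervention arm, so that the intervention's own time burden can still be reported.
5. Bring the diary description in section 10.1 into line with M8 and section 13.5.

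**Cost.** One reworded line and one added line in a diary that both arms already receive each month, plus small text changes in two sections. The drawback is that a monthly question on SSE minutes may prompt some self-examination in controls, who get no reminders, and so narrow the contrast tested in section 13.4.2. The documents do not show how large that effect would be. It is tempered because the diary is already meant to cover self-monitoring behaviours in both arms.
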